8.3 Secondary outcomes

Clinical outcomes

2. LBR at 24 months post-randomisation;
3. Time from randomisation to live birth (LBR);
4. Time from randomisation to pregnancy;
5. Clinical pregnancy (an observation of viable intrauterine pregnancy with a positive heart pulsation seen on ultrasound at/after 8 weeks gestation); miscarriage (spontaneous pregnancy loss, including pregnancy of unknown location (PUL), prior to 24 weeks gestation); premature labour (labour that happens before the 37th week of pregnancy); multiple birth (multiple live births per mother, e.g. twins or triplets etc.); still birth (delivery of a still born foetus showing no signs of life after 24 weeks gestation); and ectopic pregnancy rates (pregnancy outside the normal uterine cavity);
6. Detail of hysteroscopy received, including: number of hysteroscopic procedures received, duration of time post-surgery abstaining from sexual intercourse, type of resection performed (i.e. use of electrical energy device, morcellation devices and others). This applies to intervention arm only;
7. Patient satisfaction. A questionnaire will be designed with input from our PPI co-applicants and the Jessop Wing - Reproductive Health Research Public Advisory Panel to assess general patient satisfaction with the fertility treatments received since randomisation into the trial. The questionnaire will be sent to intervention arm participants and will concentrate on a) waiting time for treatment, b) satisfaction and tolerability of procedures received, c) thoughts on pre and post procedure information provided, d) psychological support, e) logistical family implications of surgery, f) procedure related anxiety;
8. Details of fertility treatments received, including details of medications received (e.g. clomid) and assisted reproductive techniques received (e.g. type of treatment, fresh or frozen cycle, quality and number of embryos transferred during IVF, IUI or ICSI cycle);

9. Incorrect diagnosis/absence of abnormalities at surgery. Where techniques other than diagnostic hysteroscopy have been used to visualise the endometrial polyp or submucosal fibroid, data will be collected regarding any false diagnoses of endometrial polyps/submucous fibroids;
10. Type of submucous fibroid (type 0, 1, or 2);
11. Number of participants in the control arm who undergo resection.
12. COVID-19 vaccination status (1st, 2nd, booster, approximate date and type of vaccine);

Safety outcomes

13. Adverse events due to procedure related and gynaecological/obstetric related complications (see section 10)

Health Economics

14. Health resource use of the participant measured at baseline, 6, 15 and 24 months post randomisation.
15. Patient costs measured following hysteroscopy for participants randomised to hysteroscopic resection
16. Cost per live birth gained.

8.4 Long term outcomes

- 1) Number of live births, miscarriages, terminations and still births,
- 2) Details of fertility treatment and;
- 3) Detail of hysteroscopic removal of submucous fibroids/endometrial polyps.

9. Assessments and study procedures

The schedule for data collection is summarised in Table 2. Data will be collected at specified time points from various sources including patient medical notes by **trained** members of the clinical research team and patient questionnaires, which may be completed in person, by post, by telephone/video call or online. Data collected directly by sites e.g. from medical notes, from the patient in person or by telephone/video call will be entered into the trial database by a trained member of the clinical research team. Every effort should be made to collect and enter data onto the database (Prospect) within +2 weeks of the due date (Directly post-hysteroscopy, 6, 15, 24 months +2 weeks). All contact attempts should be recorded on the database. When contacting the patient via the telephone a standard proforma (**document: study proforma**) will be used to

standardise the collection of information across all units. Data collected using the online system will be imported into the trial database by a member of the CTRU.

9.1 Study assessments schedule

Data will be collected at the time points listed below. Follow-up time points should be measured from the date of randomisation. A process flow diagram for data collection is provided in Appendix 1.

Eligibility assessment

Potential or fully eligible participants will be identified initially from medical notes and / or a database search. The site is required to follow the procedures used in their usual pathway for diagnosis and measurement of fibroids and polyps (see examples given in section 5.3.1).

Baseline

Following consent and prior to randomisation baseline data will be collected from participants. They will be asked a series of demographic, health resource use and COVID-19 vaccination status questions either in person during a clinic appointment, or by telephone / video call with a member of clinical research site staff. The questions may also be completed online. Data such as fertility markers, previous fertility treatments, type of infertility, miscarriage and detail of uterine abnormalities may be sought from the patient's medical records.

Intervention delivery – Hysteroscopic Resection

- Women randomized to the intervention arm will have the hysteroscopic procedure arranged as per local procedures.
- Following hysteroscopic resection fertility treatment will commence as planned

Directly Post-hysteroscopy (applies to the intervention arm only)

The clinical person performing the hysteroscopy procedure will be asked to complete a series of questions detailing the procedure which will be entered into the trial database. This will include details of the uterine abnormality (including size, grade and any misdiagnoses discovered during/after the procedure), any complications occurring during the procedure, detail of the techniques used (e.g. bipolar or monopolar resectoscopes, hysteroscopic morcellators or scissors or polyp snares), length of procedure and clinical staff involved. The site will also be asked to

record the number of pre- and post-operative appointments related to the intervention. These questions will apply to patients allocated to the intervention arm only.

Participants will be asked to complete:

A) the Patient Satisfaction Questionnaire (Document: Patient Satisfaction Questionnaire), which will ask questions about the patients' experiences of;

- a) Waiting time for treatment
- b) Satisfaction and tolerability of procedures received
- c) Thoughts on pre and post procedure information provided
- d) Psychological support
- e) Logistical family implications of surgery
- f) Procedure related anxiety.

B) the Patient Costs Questionnaire

These questionnaires can be completed either in person during a clinic appointment, by telephone / online, or video call with a trained member of site staff. The questionnaire may be sent directly to the participant from the CTRU via post or online.

Intervention follow-up

At 6 months post randomisation the research nurse/midwife will contact the patient to:

- Collect Adverse Events information
- Determine the length of time post-surgery abstaining from sexual intercourse

Additionally at 6 months, the research nurse/midwife/Associate PI/Dr will record the following information from patient medical notes and / or via telephone contact with the participant in line with CTRU SOPs;

- If pregnancy has occurred - time to pregnancy, pregnancy rate, miscarriage, ectopic pregnancy; adverse events; details of fertility treatments received and COVID-19 vaccination status.

The Health resource use questionnaire will be sent directly to the patient from the CTRU via post or online.

Treatment as usual - (No hysteroscopic resection)

Women randomised to 'treatment as usual' will continue with their fertility treatment as planned and will **NOT** receive the hysteroscopic resection.

Treatment as usual follow-up

At 6 months the research nurse/midwife/Associate PI/Dr will contact the patient to:

- Collect adverse event information.
- At 6 months post randomisation the research nurse/midwife/Associate PI/Dr will record the following (if applicable) from patient medical notes and / or via information collected from the telephone contact with the participant in line with CTRU SOPs; If a pregnancy has occurred - time to pregnancy, pregnancy rate, miscarriage, ectopic pregnancy; adverse events; details of fertility treatments received; and COVID-19 vaccination status.

The health resource use questionnaire will be sent directly to the patient from the CTRU via post or online.

Follow up at 15 and 24 months post-randomisation in both trial arms

15 months - Primary outcome

At 15 months post randomisation the research nurse/midwife/Associate PI/Dr will record the following information from the patients' medical notes and or via information collected from the telephone contact with the participant:

- The primary outcome (live birth rate)
- Time to live birth, time to pregnancy, pregnancy rate, miscarriage, premature labour, multiple birth, still birth, ectopic pregnancy, adverse events, details of fertility treatments received, COVID-19 vaccination status and health resource use.
- Adverse event information

The health resource use questionnaire will be sent directly to the patient from the CTRU via post or online.

24 month post-randomisation (and up to LPLV)

Members of site staff will be asked to record the following from patients' medical notes and / or telephone contact with the participant;

- Adverse event information
- Time to live birth, time to pregnancy, pregnancy rate, miscarriage, premature labour, multiple birth, still birth, ectopic pregnancy, adverse events, details of fertility treatments received and COVID-19 vaccination status.

The health resource use questionnaire will be sent directly to the patients from the CTRU via post or online.

Table 2 – Data collection time points

	Eligibility assessment	Baseline/ randomisation	Directly post-hysteroscopy #	6 months*	15 months*	24 months*	Post 24 months to Last Patient Last Visit (LPLV)	Long term (minimum 5 years post randomisation)
Demographics – age, fertility markers, previous fertility treatment received, type of infertility (infertility/recurrent miscarriage), BMI, smoking status.	MN	IP/MN						
Details of uterine abnormalities (size, grade)	MN	MN	MN					
Patient satisfaction			Q#					
Live birth rate (primary outcome)					T/MN (primary outcome)	T/MN		MN/NHSD
Time to live birth					T/MN	T/MN	MN	
Time to pregnancy				MN	T/MN	T/MN	MN	MN/NHSD
Pregnancy rate				MN	T/MN	T/MN	MN	MN/NHSD
Miscarriage				MN	T/MN	T/MN	MN	MN/NHSD
Premature labour					T/MN	T/MN	MN	

HELP Fertility?

Multiple birth					T/MN	T/MN	MN	
Still birth					T/MN	T/MN	MN	MN/NHSD
Ectopic pregnancy				T/MN	T/MN	T/MN	MN	
Adverse events; obstetric, gynaecological or procedure related complications			IP/T/MN	T and MN	T and MN	T and MN	MN	
Obstetric outcomes				T/MN	T/MN	T/MN	MN	
Details of hysteroscopy received (intervention arm only)			MN	MN	MN	T/MN	MN	MN/NHSD
Details of fertility treatments received (clomid, IVF, IUI etc.)				MN	MN	MN	MN	MN/NHSD
Health resource use,		Q/MN		Q/MN	Q/MN	Q/MN		
Patient cost questionnaire			Q					
Time post surgery abstaining from sexual intercourse [#]				T/Q				
COVID-19 vaccination status (1 st , 2 nd , booster, approximate date and type of vaccine)		T/Q		T/Q	T/Q	T/Q	T/Q	

HELP Fertility?

* Time points measured from randomisation

Intervention arm only

IP = in person, MN = medical notes

T = telephone contact with patient

Q = questionnaire, administered via post/email/online

NHSD = NHS Digital

Long term follow-up

Long term follow-up data will be collected 5 years after the final patient was recruited in one of two ways;

- 1) The clinic / hospital in which participants were randomised will be asked to check the medical records of those who gave consent for long term data collection. If the patient commenced treatment elsewhere, telephone or postal contact may be made with the participant by a member of the clinical research team.
- 2) An application will be made to NHS Digital requesting access to data from those who have agreed to this on the consent form. The names, date of birth and NHS number will be sent to NHS Digital for data linkage. Accessing data from NHS Digital is likely to result in increased data completeness compared to following up participants manually over this time frame, due to the likelihood of participants changing address and the risk of a low response rate (if followed up via questionnaire) or being discharged from the recruiting centre and receiving treatment/maternity care at another hospital (if followed up using local medical records).

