6.1 Patients randomised to Intervention Group

Hysteroscopic resection of submucous fibroids and endometrial polyps is currently undertaken routinely in the NHS for women suffering from miscarriage or infertility.

In order for this study to be applicable to the wider NHS, a pragmatic approach will be taken, and hence we will accommodate local hysteroscopic procedures conducted at the participating centres using existing surgical techniques and setups. Techniques will include the use of bipolar or monopolar resectoscopes, hysteroscopic morcellators or scissors or polyp snares. The procedure may be performed in an outpatient or inpatient setting. For large abnormalities, further surgical procedures may be required. Type 0 and Type I submucous fibroids are more easily resectable than Type II. Clinical / operator judgement will be used to determine the intra-cavitary portion that is resectable for Type II fibroids. As per usual practice, women randomised to receive the intervention will be asked to use contraception prior to hysteroscopy taking place, if applicable. A pregnancy test may also be undertaken. This is in line with routine clinical care and the World Health Organisation (WHO) checklist prior to resection (33). In the event that a patient allocated to intervention has a positive pregnancy test before receiving hysteroscopic resection, the patient will remain in the trial and followed-up as per the schedule in 9.1.

Scheduling treatment

For participants allocated to the intervention group, sites should aim to schedule the appointment for hysteroscopic resection within the 18-week patient pathway. However, with the current COVID-19 pandemic the procedure should be scheduled within the site's own current guidelines. Participants expecting to receive other fertility treatments e.g. IVF, ovulation induction, IUI, Donor Sperm Insemination, ICSI or medications e.g. clomid, should commence with this treatment as soon as possible following hysteroscopic resection. This does not include any research infertility interventions as these are exclusion criteria.

Compliance

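### Time abstaining after surgery is asked once, six months from randomisation, so it is lost or cut short when surgery is late or repeated; the post-operative appointment count can likewise omit later visits

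*Protocol*

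**What the plan says.** **Abstinence.** Section 8.3 of the protocol makes this part of secondary outcome 6, which includes "number of hysteroscopic procedures received, duration of time post-surgery abstaining from sexual intercourse, type of resection performed". Section 9.1 places it at one contact, introduced by "At 6 months post randomisation the research nurse/midwife will contact the patient to", where staff are to "Determine the length of time post-surgery abstaining from sexual intercourse". The Table 2 row "Time post surgery abstaining from sexual intercourse" has a single entry, by telephone or questionnaire, under 6 months. The same section states that "Follow-up time points should be measured from the date of randomisation".

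**Timing of surgery.** Section 6.1 says "sites should aim to schedule the appointment for hysteroscopic resection within the 18-week patient pathway", but then that "with the current COVID-19 pandemic the procedure should be scheduled within" each site's own current guidelines. No latest date is set. The same section notes that large abnormalities may need further procedures. Section 8.1 expects the pandemic to affect waiting times. In Table 1, fewer than 80% treated before 3 months is only amber, and red does not apply. Section 11.2 counts surgery up to six months as per protocol.

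**Appointments.** Under the directly post-hysteroscopy heading in section 9.1, sites are asked to "record the number of pre- and post-operative appointments related to the intervention". The introduction to section 9 sets a target of two weeks after the due date for collecting and entering data. No later time point names these appointments, and they have no row in Table 2.

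**The concern.** Abstinence is a duration that starts at surgery, but the only question about it is fixed to randomisation. Three groups of women are exposed:

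- Women first operated on after the 6-month contact have no scheduled question at all.
- Women operated on shortly before it may be asked while the period is still running.
- Women who have a second procedure after it have no question about the second period.

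The losses fall on the women treated latest, so the recorded durations would describe the earlier-treated women. For couples trying to conceive naturally, time abstaining is one part of the delay between allocation and a chance of pregnancy, which is why the item is of interest.

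The appointment count has a related weakness. A count made at, or within about two weeks of, the procedure cannot include visits that come later, and it feeds the cost of the intervention.

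**Working it through.** The protocol gives no figure for the share of women affected, so there is nothing of its own to reproduce. The check is calendar arithmetic, followed by an illustration on assumed waits.

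**1. Time between surgery and the question.** With 52.18/12 = 4.348 weeks per month, 6 months is 26.1 weeks.

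| Surgery at | Weeks until the 6-month contact |
|---|---|
| Randomisation (pathway 2, sections 5.3 and 7) | 26.1 |
| 3 months (Table 1) | 26.1 − 13.0 = 13.0 |
| 18 weeks (section 6.1) | 26.1 − 18 = 8.1 |
| 6 months (per-protocol limit, section 11.2) | 0, or 2 with the collection window |
| Later | no scheduled question |

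The item works for surgery on schedule and fails for surgery near or after month 6.

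**2. Share operated on after month 6 (assumed waits).** Let s be the share treated by 3 months.

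*Exponential wait:* P(T > 6) = (1 − s)^(6/3) = (1 − s)².

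- s = 0.80: 0.20² = 0.04, about 11 of the 280 randomised to resection in one trial (560/2)
- s = 0.60: 0.40² = 0.16, about 45 of 280
- s = 0.50: 0.50² = 0.25, about 70 of 280
- s = 0.40: 0.60² = 0.36, about 101 of 280

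*Log-normal wait, σ = 0.6:* μ = ln 3 − σ·z(s), and P(T > 6) = 1 − Φ((ln 6 − μ)/σ).

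- s = 0.80: μ = 1.099 − 0.6 × 0.842 = 0.594; (1.792 − 0.594)/0.6 = 1.997; P = 0.023
- s = 0.60: μ = 1.099 − 0.6 × 0.253 = 0.947; (1.792 − 0.947)/0.6 = 1.409; P = 0.079

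At the green criterion of 80% by 3 months, the two shapes give about 2% and 4%. At 60% they give about 8% and 16%.

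**3. Share operated on shortly before the contact.** This also needs an assumed length of abstinence, which the protocol does not give. Taking 4 weeks as an example, the exponential model puts 6.6% after, or within 4 weeks before, the contact at s = 0.80. That is 6.6 − 4.0 = 2.6 percentage points possibly cut short. At s = 0.60 the corresponding total is 21.2%.

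**4. Whether another row covers abstinence.** Table 2 repeats details of the hysteroscopy received at 6, 15 and 24 months and up to the last patient's last visit. The source is medical notes, with telephone added only at 24 months. Abstinence is reported by the patient and has its own row, which stops at 6 months.

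**5. Whether another row covers appointments.** Table 2 lists health resource use from questionnaire and notes at 6, 15 and 24 months. Section 11.2 limits the questionnaire to the preceding 3 months, so those forms cover roughly months 3–6, 12–15 and 21–24. Visits before month 3 or in months 6–12 fall outside the questionnaire. The protocol states no such limit for the notes, but neither source names post-operative appointments.

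**The case against.** The strongest reply is that the schedule works for most women as planned. Surgery at 3 months or 18 weeks leaves 13 or 8 weeks, and pathway 2 leaves the full six months. That stands. A reader might infer that the two items are timed so that they generally miss what they measure, and the calendar does not support this. The abstinence gap depends on late or repeat surgery.

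A reader might also want one headline share, and a wide range can be produced. If the median wait is set at 18 weeks, a log-normal model puts 18% to 27% after month 6 (σ = 0.4 and 0.6). But sites are asked to aim within the 18-week pathway, so making it the median is a stress case. The shape and spread of the waits are also assumptions.

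On appointments, a reader might infer that the cost per live birth will look too favourable to resection. Omitted visits would push the intervention cost down. However, the protocol gives no number, timing or cost of post-operative visits, the two weeks is a target and not a lock on the form, and the notes-based resource-use data may recover the visits. No bias in the cost result is shown.

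Finally, abstinence is one descriptive component of an intervention-arm outcome that no analysis in section 11.2 uses. For women going on to assisted conception it is a weak measure of delay. Surgical delay itself is tracked by the 3-month criterion, and the timing of the primary endpoint may be revised in response. This limits the importance of the point. It does not supply the missing question.

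**Conclusion.** The point holds as a minor, inexpensive improvement. Followed as written, the schedule leaves a named component of secondary outcome 6 uncollected for women whose surgery or repeat surgery comes after month 6, and possibly truncated for those treated just before. The protocol itself foresees both delay and repeat procedures.

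The size is unknown because no waiting-time distribution is given. About 2% to 4% operated on after month 6 is a reasonable illustration if 80% are treated by 3 months, and the share rises as waits lengthen. These figures rest on assumed exponential and log-normal waits. Any figure for truncation rests further on an assumed length of abstinence.

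The appointment count is a secondary point: later visits can be omitted, by an amount the document does not allow to be estimated. The primary outcome, sample size and error rates are not affected.

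**What to change.** Keep the 6-month abstinence question. In Table 2 and the CRF, repeat it at the existing 15-month contact, and at 24 months if needed, for women whose surgery or repeat surgery took place after the previous contact or whose abstinence was still running at that contact. Record the date of the procedure to which each answer refers.

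For post-operative appointments, keep the field on the post-hysteroscopy form and add a named field to the medical-notes reviews already scheduled at 6 and 15 months, so that the count is updated.

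The cost is wording in Table 2 and a few conditional CRF fields, with no new contacts and no change to clinical care. The one drawback is longer recall for women first asked at 15 or 24 months.

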9.2 Participant withdrawal from randomised treatment

Participants may wish to withdraw from the randomised study treatment i.e. women allocated to the control arm who later wish to undergo resection and women allocated to the intervention arm who later do not wish to undergo resection. There may also be a clinical need to withdraw participants from their randomised treatment allocation. In such cases centres will explain the importance of remaining in study follow-up to participants, and that changes to planned treatment need not imply withdrawal from the trial. In such cases all study outcomes will continue to be collected. Nevertheless, if participants do not wish to remain in the trial their decision must be respected.

If the participant explicitly states their wish not to contribute further data to the trial, this is considered withdrawal from the trial, see 9.3.

